11.2. Assessment of Adverse Events and Serious Adverse Events

The investigator or qualified sub-investigator is responsible for assessing AEs and SAEs for causality and for final review and confirmation of accuracy of event information and assessments.

11.2.1. Assessment of Causality for Study Drugs

Study drugs in this context include E/C/F/TAF, F/TAF, R/F/TAF or any other Gilead or non-Gilead ARV used during the study. The investigator or qualified sub-investigator is responsible for assessing the relationship to drug therapy using clinical judgment and the following considerations:

- **No:** Evidence exists that the event has an etiology other than the drug.
- **Yes:** There is a reasonable possibility that the event may have been caused by the medicinal product.

It should be emphasized that ineffective treatment should not be considered as causally related in the context of AE reporting.

11.3. Special Situations Reports

11.3.1. Definitions of Special Situations

Special situation reports (SSR) for study drugs (study drugs in this context include E/C/F/TAF, F/TAF, R/F/TAF or any other Gilead or non-Gilead ARV used during the study) include reports of abuse, drug interactions, counterfeit or falsified medicine, exposure via breastfeeding, lack of effect, medication error, misuse, occupational exposure, off-label use, overdose, pregnancy, product complaints, transmission of infectious agents via the product, and unexpected benefit. Definitions are examples are provided below:

- **Abuse:** Persistent or sporadic intentional excessive use of a medicinal product by a patient.
- **Drug interactions:** Any reports of drug/drug, drug/food, or drug/device interactions.
- **Counterfeit or falsified medicine:** Any medicinal product with a false representation of: a) its identity, b) its source, or c) its history.
- **Exposure via breastfeeding:** Reports of any exposure to a medicinal product during breastfeeding.

- Lack of effect: A report of a situation where there is apparent failure of the medicinal product or medical technology to bring about the intended beneficial effect on individuals in a defined population with a given medical problem, under ideal conditions of use.
- Medication error: Any unintentional error in the prescribing, dispensing, preparation for administration or administration of a medicinal product while the medication is in the control of a healthcare professional, patient or consumer.
- Misuse: Use of a medicinal product that is intentional and inappropriate not in accordance with its authorized product information.
- Occupational exposure: Exposure to a medicinal product as a result of one's professional or non-professional occupation.
- Off-label use: Where a medicinal product is intentionally used by a Health Care Professional for a medical purpose not in accordance with the authorized product information with respect to indication, dose, route of administration, or patient population (e.g., the elderly).
- Overdose: Administration of a quantity of a medicinal product given per administration or cumulatively which is above the maximum recommended dose in the product labelling.
- Pregnancy reports (maternal pregnancy and partner pregnancy): Reports of pregnancy following maternal or paternal exposure to the product.
- Product complaint: Complaints arising from potential deviations in the manufacture, packaging, or distribution of the medicinal product.
- Unexpected benefits: An unintended therapeutic effect where the results are judged to be desirable and beneficial.
- Transmission of infectious agents via the product: Any suspected transmission of an infected agent through a Gilead medicinal product.

11.3.2. Instructions for Reporting Special Situations

11.3.2.1. Instructions for Reporting Pregnancies

All pregnancies that occur while exposed to the study drugs (study drugs in this context include E/C/F/TAF, F/TAF, R/F/TAF or any other Gilead or non-Gilead ARV used during the study) and the outcome of the pregnancy are to be reported to Gilead PVE using the pregnancy report form within 3 calendar days of becoming aware of the pregnancy.

The pregnancy itself is not considered an AE nor is an induced elective abortion to terminate a pregnancy without medical reasons.

Any premature termination of pregnancy (eg, a spontaneous abortion, an induced therapeutic abortion due to complications or other medical reasons) must be reported within 3 calendar days as an SAE. The underlying medical reason for this procedure should be recorded as the AE term.

A spontaneous abortion is always considered to be an SAE and will be reported as described in Section 11.4. Furthermore, any SAE occurring as an adverse pregnancy outcome post study must be reported to Gilead PVE.

The outcome should be reported to Gilead PVE using the pregnancy outcome report form.

11.4. Investigator Requirements and Instructions for Reporting ADRs, SADR, and SSRs to Gilead

All fatal events (regardless of causality) and all related non-serious AEs (ie, ADRs), and related SAEs (ie, SADR) occurring after the subject consents to participate in the study (ie, signing informed consent) until study completion, loss to follow-up, withdrawal of consent, death or 4 weeks after discontinuation of study drugs (study drugs in this context include E/C/F/TAF, F/TAF, R/F/TAF or any other Gilead or non-Gilead ARV used during the study), whichever comes first, will be reported on the AE/SAE electronic case report form (eCRF). Special situations reports (SSRs) will be recorded on the Gilead Special Situation Report Form. Pregnancy reports will be recorded on the pregnancy eCRF.

Timelines for reporting ADRs, SADR, and SSRs to Gilead are as follows:

- Within 3 calendar days of knowledge of all fatal events and SADR
- Within 30 calendar days of knowledge of the ADRs and SSRs

Details of the methods for reporting ADRs, SADR, and SSRs to Gilead PVE will be described in the CRF completion Guidelines.

If reporting of events is by electronic submission via eCRF, this method must always be used unless the eCRF system is not functioning at which time site personnel should record details of the ADR, SADR, or SSR on the appropriate paper reporting form (the *Non-Interventional Study AE/SAE Report Form* or the *Non-Interventional Study Special Situation Report Form*) and submitted by fax or e-mail, within the timelines given above, to:

PPD [REDACTED]

Fax: PPD [REDACTED]

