- To describe physical and mental health-related quality of life, health status, and treatment satisfaction using standardized questionnaires Health Survey Short Form (SF-36), HIV Symptom Index, and HIV Treatment Satisfaction Questionnaire
- To describe health care resource utilization (eg, number of hospitalizations, number of physician visits)

The above parameters will be evaluated in the overall cohort and in various subgroups (eg, treatment-naïve subjects versus treatment-experienced subjects, age (< 50 years, ≥ 50 years), presence of specific comorbidities, sex).

The collection of ADR/SADR reflects the real-life situation, in which the treating physician with best knowledge of his patient assesses whether an observed event could be related to a given treatment. In this way, the study will collect safety data that is reflective of the real-life setting in which it is conducted.

Study Design:

Prospective, non-interventional, observational cohort study. Enrolled subjects will be documented using an electronic case report form (eCRF) by the participating sites. Each enrolled subject will be followed for 24 months (irrespective of regimen changes).

Population:

The study will enroll 900 adult (age ≥ 18) treatment-naïve and treatment-experienced HIV-1 infected subjects initiating treatment with E/C/F/TAF, F/TAF or R/F/TAF in routine care.

E/C/F/TAF arm: 150 treatment-naïve and 150 treatment-experienced subjects, at least 20% of the total 300 subjects will be ≥ 50 years of age at enrollment

F/TAF arm: 150 treatment-naïve and 150 treatment-experienced subjects, all 150 treatment-experienced subjects will be ≥ 50 years of age at enrollment

R/F/TAF arm: 150 treatment-naïve and 150 treatment-experienced

subjects, at least 20% of the total 300 subjects will be ≥ 50 years of age at enrollment

Participating study sites (hospitals and private practitioners) are specialized on treating HIV patients. All study sites are located in Germany.

Variables:

Prior to E/C/F/TAF, F/TAF or R/F/TAF treatment initiation (baseline):

Gender, year of birth, body weight and height

Race

Date of HIV-1 diagnosis

CDC stage

Co-morbidities as available from medical records

Laboratory parameters as available from medical records:

- HIV-1 RNA and limit of detection of the used assay
- CD4 cell count
- AST, ALT, gamma-GT
- Albumin
- Urine albumin/creatinine ratio (UACR), urine protein/creatinine ratio (UPCR)
- Serum total protein
- Triglycerides
- Total cholesterol

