9. RESEARCH METHODS

9.1. Study Design

This non-interventional study does not influence the treatment decisions made by the participating physicians. Subjects can be enrolled in this study after the physician has decided to treat a specific subject with E/C/F/TAF, F/TAF or R/F/TAF in accordance with the approved respective SmPCs. All treatments will be prescribed according to local treatment guidelines and/or routine clinical practice. The treating physician will make all treatment decisions and will provide prescriptions for his/her patients. There will be no study-specific procedures.

The study is designed as a multicenter, non-interventional observational cohort study, in accordance with the German Drug Act (§63f AMG). It is planned to enrol a total of 900 adult (age ≥ 18) HIV-1 infected subjects initiating treatment with E/C/F/TAF (n=300), F/TAF (n=300) or R/F/TAF (n=300) in routine care. The study will enroll approximately 150 treatment-naïve and 150 treatment-experienced subjects in each arm.

Data collection will be performed by manual entry of data from the patient's medical file and questionnaires to a computer-based electronic case report form (eCRF). No patient initials will be included.

Data will be prospectively collected for each enrolled subject for approximately 24 months. In case of E/C/F/TAF, F/TAF or R/F/TAF discontinuation the date of discontinuation, reasons for discontinuation (eg, patient wish, adverse reaction, insufficient efficacy) and subject's new ART will be collected. The subject will remain in the study and will be continuously documented with the new ART until premature end of documentation (eg, due to lost to follow up) or until reaching the defined end of documentation approximately 24 month after enrollment.

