Anti-retroviral therapy adherence (VAS scale and number of missed doses during the last 4 and 30 days). The questionnaire with the VAS scale and the questions about the missed doses will be handed to the patients, filled in by the patients and the patient will put the questionnaire into an envelope. Only the closed envelope will be returned to the site staff. The closed envelope which only contains the subject number as identifier will be sent by the site to the CRO for data entry. The site will not know any information the patient entered into the questionnaire.

In case of E/C/F/TAF, F/TAF or R/F/TAF discontinuation: date of discontinuation, reasons for discontinuation (eg, patient wish, adverse reaction, insufficient efficacy) and subject's new ART. The subject will remain in the study and will be continuously documented with the new ART until premature end of documentation (eg, due to lost to follow up) or until reaching the defined end of documentation approximately 24 month after enrollment.

Changes in co-medications as available from medical records

Laboratory parameters: see baseline

New AIDS-defining events (CDC class C, excluding CD4 cell count < 200 cells/ μ L)

Changes in co-morbidities/co-infections

ADRs and SADR for all ARV drugs used in the study

Special situations reports as appropriate

Only approximately 12 months and 24 months after starting E/C/F/TAF, F/TAF, or R/F/TAF therapy: Blood pressure and cardiovascular and renal risk factors (eg, family history of angina/heart attack, smoking status, intravenous drug use)

HIV Symptom Index

HIV Treatment Satisfaction Questionnaire (only for treatment experienced subjects and only approximately 3 months, 6 months and 12 months after E/C/F/TAF, F/TAF or R/F/TAF therapy initiation)

SF-36

In case of virologic failure: resistance status as available

Resource Utilization (number and duration of hospitalizations, number of appointments with HIV-treating physician and with other physician types between the documented visits)

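### Section 11.4 ends death and ADR reporting 4 weeks after all ART is stopped and has no rule for resumption, although subjects are documented to about 24 months

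*Protocol*

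**What the plan says.** Protocol Section 11.4 tells sites what to report on the AE/SAE form and until when. The events are "All fatal events (regardless of causality) and all related non-serious AEs (ie, ADRs), and related SAEs (ie, SADR"). Reporting starts at consent and ends at study completion, loss to follow-up, withdrawal of consent, death or "4 weeks after discontinuation of study drugs". The sentence closes with the rule "whichever comes first, will be reported on the AE/SAE electronic case report form (eCRF"). A parenthesis inside it defines the term: "study drugs in this context include E/C/F/TAF, F/TAF, R/F/TAF or any other Gilead or non-Gilead ARV used during the study".

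Four other places set the length of follow-up and the scope of safety collection:

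- The synopsis (Section 4, Study Design): "Each enrolled subject will be followed for 24 months (irrespective of regimen changes").
- Section 9.1, on discontinuation of the initial product: "The subject will remain in the study and will be continuously documented with the new ART until premature end of documentation", or until about 24 months after enrolment.
- Section 9.3, among the follow-up variables: "ADRs and SADR for all ARV drugs used in the study".
- The opening of Section 11, which likewise sets the scope of ADR, SADR and special-situation collection as every ARV used during the study.

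Section 8 makes the rates of ADRs and SADRs for the three products a secondary objective. It names no all-cause mortality rate.

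**The concern.** The end of safety reporting depends on treatment, while the end of documentation is meant not to. The two can separate in any subject who goes without ART for more than 4 weeks, and two things are then at stake.

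First, death is the only outcome the protocol asks for regardless of cause. If a subject stops all ART and dies some months later, Section 11.4 read literally does not call for that death on the AE/SAE form, even though the site is still documenting the subject. Subjects who stop all treatment are a selected group, so what is missed is not a random sample of deaths.

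Second, an earliest-of-several-dates rule, once triggered, has been met for good. Section 11.4 does not say what happens when a subject restarts an ARV. An ADR to the resumed drug would be outside the window under Section 11.4 and inside the scope of Sections 9.3 and 11. Sites could resolve this differently.

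**Working it through.** The plan states no figure on this point, so there is none to reproduce. The check is to compare the passages case by case and then to illustrate the scale.

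**Comparison of the passages**

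1. *Subject switches to another ARV.* The new drug is a study drug by the parenthesis in Section 11.4. On the natural reading, study drugs have not been discontinued and the 4-week limit is not triggered. This agrees with Sections 9.1, 9.3 and 11.
2. *Subject stops all ARVs and stays off.* The limit is triggered 4 weeks later. Deaths, ADRs and SADRs after that date are outside Section 11.4. The synopsis sets 24 months of follow-up irrespective of regimen changes, and Section 9.1 names stopping ART neither as an end of documentation nor as an example of a premature one. Section 9.1 does assume that a new ART follows, so it does not address this subject in so many words.
3. *Subject stops all ARVs for more than 4 weeks and then resumes.* The limit has already been triggered and Section 11.4 contains no reopening. Sections 9.3 and 11 still require ADRs for the resumed ARV. The passages conflict.

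**Scale, for illustration only**

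Inputs:

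- From the protocol: 900 subjects, 24 months each, so 900 × 2 = 1,800 planned person-years; 4-week limit w = 28 days = 28/30.4375 = 0.92 months.
- Assumed, because the protocol gives no such rate: a share f stops all ARVs permanently, at times uniform over 24 months, and every subject is otherwise documented to month 24.

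A subject who stops at month t has 24 − w − t months outside the window, if that is positive. Averaged over a uniform t, the share of planned subject-time outside the window is

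f × (24 − w)² / (2 × 24²) = f × 23.08² / 1,152 = f × 0.462.

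| f assumed | Subjects of 900 | Share of subject-time outside | Person-years of 1,800 |
|---|---|---|---|
| 1% | 9 | 0.5% | 8 |
| 2% | 18 | 0.9% | 17 |
| 5% | 45 | 2.3% | 42 |

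In this illustration all of the excluded time is off drug, so few new ADRs would be expected in it. It measures exposure to missed deaths rather than to missed ADRs. ADRs are at risk in the third case, for which the documents offer no basis for an estimate.

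**The case against.** The strongest reply is that the protocol largely answers the concern. The definition of study drugs in Section 11.4 is broad and recurs in Sections 11.2.1, 11.3.1 and 11.3.2.1. Ending ADR collection after a 4-week run-out is an ordinary design choice, since an ADR needs a causal link to a product. Section 9.3 continues to document laboratory values, AIDS-defining events, co-morbidities and hospitalisations. A resumed drug is again an ARV used during the study, so Section 11 can be read as covering it. Few subjects are affected.

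Most of this stands, and it rules out three stronger conclusions that a reader might draw:

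- *That all ADRs after a switch are lost.* This requires the window to close when any one ARV is stopped. Section 11.4 does not literally say all ARVs, so the reading is possible. But it would make the inclusion of other ARVs in the definition almost pointless, and it contradicts Sections 9.3 and 11. With 10% to 30% of subjects switching (assumed), the same formula gives 4.6% to 13.9% of subject-time. That figure depends wholly on a reading the documents do not support.
- *That late deaths drop out of the safety rates.* The objective is ADR and SADR rates. A death judged unrelated was never part of them; its absence affects fatal-event reporting only.
- *That events are divided by the wrong person-time.* No 24-month denominator is stated. The glossary defines a rate by person-time within an exposure category, and further detail may properly be left to the SAP.

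The reply does not remove two gaps. Nothing extends any-cause death reporting to the end of documentation for a subject off ART, and the operative reporting section is silent on resumption where the scope statements are not.

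**Conclusion.** The point holds in a narrow form. On the natural reading of Section 11.4, switchers remain under safety reporting. A subject off all ART for more than 4 weeks leaves fatal-event reporting while still in documentation, and the text has no rule for ADRs after ART is resumed, in conflict with Sections 9.3 and 11.

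The size is small: about 1% to 2% of planned subject-time if 2% to 5% of subjects stop all ART permanently at uniformly distributed times. Both the 2% to 5% and the uniform timing are assumptions. The effect is on the completeness of death reporting and of ADRs after resumption. It does not extend to ADR/SADR rates in switchers or to the primary objective. It is worth correcting because the correction is cheap and changes what is captured.

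**What to change.** Reconcile Section 11.4 with Sections 9.1, 9.3 and 11 by stating that:

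- the safety data-collection window closes, with its 4-week run-out, only when no ARV is being taken;
- the window reopens if an ARV is resumed while the subject is still being documented;
- fatal events, regardless of causality, are recorded until the end of documentation.

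This concerns data capture only and leaves treatment decisions untouched. The person-time convention for ADR rates can stay with the SAP. The cost is a few sentences in Section 11.4 and in the CRF completion guidelines, and a small number of additional fatal-event reports.

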11.5. Gilead Reporting Requirements

Gilead is responsible for reporting and analyzing reports of all ADRs and SADR or suspected unexpected serious adverse reactions (SUSARs) for Gilead drugs as determined by country-specific legislation. Gilead may be required to report to other regulatory agencies.

Assessment of expectedness for ADRs and SADR for Gilead drugs will be determined by Gilead using reference safety information specified in the product label.

Depending on relevant local legislation or regulations, including the applicable US FDA Code of Federal Regulations, and other country-specific legislation or regulations, Gilead may be required to expedite to worldwide regulatory agencies reports of SAEs, serious adverse drug reactions (SADR), or suspected unexpected serious adverse reactions (SUSARs).

12. PLANS FOR DISSEMINATING AND COMMUNICATING STUDY RESULTS

12.1. Study Report and Publications

A clinical study report (CSR) will be prepared and provided to the applicable regulatory agencies. Gilead will ensure that the report meets the standards set out in the Guideline on Good Pharmacovigilance Practices (GVP) Module VIII. Note that an abbreviated report may be prepared in certain cases. The final CSR will be submitted within 12 months of study completion.

Annex 2. ENCePP Checklist for Study Protocols

ENCePP Checklist for Study Protocols (Revision 2, amended)

Doc.Ref. EMA/540136/2009

Study title:

Non-Interventional Real-Life Study of Effectiveness, Safety, Adherence, and Health-Related Quality of Life in Adult Patients receiving Elvitegravir/Cobicistat/Emtricitabine/Tenofovir alafenamide (E/C/F/TAF) or Emtricitabine/Tenofovir alafenamide (F/TAF) or Rilpivirine/Emtricitabine/Tenofovir alafenamide (R/F/TAF) for HIV-1 Infection in Germany

Study reference number:

GS-DE-292-1912

Section 1: Milestones	Yes	No	N/A	Page Number(s)
1.1 Does the protocol specify timelines for				
1.1.1 Start of data collection ¹				16
1.1.2 End of data collection ²				16
1.1.3 Study progress report(s)				
1.1.4 Interim progress report(s)				
1.1.5 Registration in the EU PAS register				16
1.1.6 Final report of study results.				16

Comments:

--

Section 2: Research question	Yes	No	N/A	Page Number(s)
2.1 Does the formulation of the research question and objectives clearly explain:				
2.1.1 Why the study is conducted? (e.g. to address an important public health concern, a risk identified in the risk management plan, an emerging safety issue)				17, 18
2.1.2 The objective(s) of the study?				19
2.1.3 The target population? (i.e. population or subgroup to whom the study results are intended to be generalised)				20, 21
2.1.4 Which formal hypothesis(-es) is (are) to be tested?				
2.1.5 If applicable, that there is no a priori hypothesis?				

¹ Date from which information on the first study is first recorded in the study dataset or, in the case of secondary use of data, the date from which data extraction starts.

² Date from which the analytical dataset is completely available.

Comments:

No formal hypothesis testing, comparisons between various subgroups will be done using logistic or longitudinal models.

Section 3: Study design	Yes	No	N/A	Page Number(s)
3.1 Is the study design described? (e.g. cohort, case-control, randomised controlled trial, new or alternative design)				20
3.2 Does the protocol specify the primary and secondary (if applicable) endpoint(s) to be investigated?				19
3.3 Does the protocol describe the measure(s) of effect? (e.g. relative risk, odds ratio, deaths per 1000 person-years, absolute risk, excess risk, incidence rate ratio, hazard ratio, number needed to harm (NNH) per year)				

Comments:

Section 4: Source and study populations	Yes	No	N/A	Page Number(s)
4.1 Is the source population described?				20, 21
4.2 Is the planned study population defined in terms of:				
4.2.1 Study time period?				20
4.2.2 Age and sex?				21, 22
4.2.3 Country of origin?				
4.2.4 Disease/indication?				21, 22
4.2.5 Co-morbidity?				
4.2.6 Seasonality?				
4.3 Does the protocol define how the study population will be sampled from the source population? (e.g. event or inclusion/exclusion criteria)				

Comments:

Subjects will be enrolled by sites as E/C/F/TAF, F/TAF or R/F/TAF is initiated in a patient and this patient consents to participate. 900 subjects will be enrolled and each subject documented for max. 24 months. No limitations in regard to sex, country of origin, or co-morbidities.

Section 5: Exposure definition and measurement	Yes	No	N/A	Page Number(s)
5.1 Does the protocol describe how exposure is defined and measured? (e.g. operational details for defining and categorising exposure)				20
5.2 Does the protocol discuss the validity of exposure measurement? (e.g. precision, accuracy, prospective ascertainment, exposure information recorded before the				

Section 5: Exposure definition and measurement	Yes	No	N/A	Page Number(s)
outcome occurred, use of validation sub-study)				
5.3 Is exposure classified according to time windows? (e.g. current user, former user, non-use)				20
5.4 Is exposure classified based on biological mechanism of action and taking into account the pharmacokinetics and pharmacodynamics of the drug?				21, 22
5.5 Does the protocol specify whether a dose-dependent or duration-dependent response is measured?				24

Comments:

Section 6: Endpoint definition and measurement	Yes	No	N/A	Page Number(s)
6.1 Does the protocol describe how the endpoints are defined and measured?				19
6.2 Does the protocol discuss the validity of endpoint measurement? (e.g. precision, accuracy, sensitivity, specificity, positive predictive value, prospective or retrospective ascertainment, use of validation sub-study)				26

Comments:

Section 7: Confounders and effect modifiers	Yes	No	N/A	Page Number(s)
7.1 Does the protocol address known confounders? (e.g. collection of data on known confounders, methods of controlling for known confounders)				26
7.2 Does the protocol address known effect modifiers? (e.g. collection of data on known effect modifiers, anticipated direction of effect)				26

Comments:

Section 8: Data sources	Yes	No	N/A	Page Number(s)
8.1 Does the protocol describe the data source(s) used in the study for the ascertainment of:				
8.1.1 Exposure? (e.g. pharmacy dispensing, general practice prescribing, claims data, self-report, face-to-face interview, etc.)				20
8.1.2 Endpoints? (e.g. clinical records, laboratory markers or values, claims data, self-report, patient interview including scales and questionnaires, vital statistics, etc.)				22-25

Section 8: Data sources	Yes	No	N/A	Page Number(s)
8.1.3 Covariates?				22-24
8.2 Does the protocol describe the information available from the data source(s) on:				
8.2.1 Exposure? (e.g. date of dispensing, drug quantity, dose, number of days of supply prescription, daily dosage, prescriber)				20
8.2.2 Endpoints? (e.g. date of occurrence, multiple event, severity measures related to event)				22-24
8.2.3 Covariates? (e.g. age, sex, clinical and drug use history, co-morbidity, co-medications, life style, etc.)				22-24
8.3 Is a coding system described for:				
8.3.1 Diseases? (e.g. International Classification of Diseases (ICD)-10)				26
8.3.2 Endpoints? (e.g. Medical Dictionary for Regulatory Activities (MedDRA) for adverse events)				26
8.3.3 Exposure? (e.g. WHO Drug Dictionary, Anatomical Therapeutic Chemical (ATC) Classification System)				
8.4 Is the linkage method between data sources described? (e.g. based on a unique identifier or other)				

Comments:

linkage between data sources not applicable

Section 9: Study size and power	Yes	No	N/A	Page Number(s)
9.1 Is sample size and/or statistical power calculated?				25

Comments:

Section 10: Analysis plan	Yes	No	N/A	Page Number(s)
10.1 Does the plan include measurement of excess risks?				
10.2 Is the choice of statistical techniques described?				25
10.3 Are descriptive analyses included?				25
10.4 Are stratified analyses included?				21
10.5 Does the plan describe methods for adjusting for confounding?				

Section 10: Analysis plan	Yes	No	N/A	Page Number(s)
10.6 Does the plan describe methods addressing effect modification?				

Comments:

Potential confounders/effect modifiers for multivariate analyses and respective adjustments will be addressed in the Statistical Analysis Plan

Section 11: Data management and quality control	Yes	No	N/A	Page Number(s)
11.1 Is information provided on the management of missing data?				26
11.2 Does the protocol provide information on data storage? (e.g. software and IT environment, database maintenance and anti-fraud protection, archiving)				25, 26
11.3 Are methods of quality assurance described?				26
11.4 Does the protocol describe possible quality issues related to the data source(s)?				25, 26
11.5 Is there a system in place for independent review of study results?				

Comments:

Section 12: Limitations	Yes	No	N/A	Page Number(s)
12.1 Does the protocol discuss: 12.1.1 Selection biases? 12.1.2 Information biases? (e.g. anticipated direction and magnitude of such biases, validation sub-study, use of validation and external data, analytical methods)	 	 	 	25
12.2 Does the protocol discuss study feasibility? (e.g. sample size, anticipated exposure, duration of follow-up in a cohort study, patient recruitment)				20-22
12.3 Does the protocol address other limitations?				27

Comments:

Section 13: Ethical issues	Yes	No	N/A	Page Number(s)
13.1 Have requirements of Ethics Committee/Institutional Review Board approval been described?				27

Section 13: Ethical issues	Yes	No	N/A	Page Number(s)
13.2 Has any outcome of an ethical review procedure been addressed?				
13.3 Have data protection requirements been described?				27

Comments:

Section 14: Amendments and deviations	Yes	No	N/A	Page Number(s)
14.1 Does the protocol include a section to document future amendments and deviations?				15

Comments:

Section 15: Plans for communication of study results	Yes	No	N/A	Page Number(s)
15.1 Are plans described for communicating study results (e.g. to regulatory authorities)?				35
15.2 Are plans described for disseminating study results externally, including publication?				

Comments:

Name of the main author of the protocol: PPD

Date: 04/11/2019

Signature: PPD
